cognitive behavioral relaxation techniques and found a 13.6% reduction in FIQR scores. From these studies, we estimate the difference between the yoga and structured exercise group is 17%. A between-group treatment difference of 14% reduction in symptoms represents a minimum clinically meaningful intervention effect.¹¹⁹ To be conservative, we will assume a 14% difference between treatment groups. The absolute score difference at 3 months is estimated to be approximately 7 points (6.79, 14% of 48.3). Assuming a common standard deviation of 17.6 and using a two-sample t-test, we will need 107 evaluable subjects in each arm to detect such a difference with >80% power and 5% Type I standard error rate.

We recognize the correlation of outcomes from subjects within the same yoga or exercise class may reduce the effective sample size compared to the same sample with independent observations. This possible “clustering effect” seen in group delivered interventions has implications for power. We have no preliminary data to estimate the intra-cluster correlation (ICC) for participants within the same group. However, based on similarly designed published studies, we expect the ICC to be relatively small and balanced across the two treatment arms since the cluster sizes will be similar.¹²⁰ Conservatively, we assume an ICC of 0.02 for both treatment groups. With 8 subjects per treatment group/class or cluster, the design effect is $1 + (8-1) \times 0.02 = 1.14$. Therefore, we will inflate our sample size by 14% to accommodate the potential clustering effects. We then need 122 evaluable subjects in each arm. With a conservative 20% attrition, we will then need $(122 \times 2) / 0.80 = 306$ subjects (153 in each arm).

D9b. Data analysis: Baseline characteristics of POYSE sample

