Since the primary outcome (FIQR total score) is measured repeatedly at baseline, 1, 3, 6, and 9 months, we will fit a repeated measurement analysis of covariance (ANCOVA) model with the four post baseline (1, 3, 6, and 9 months) FIQR total score as the response variables. The main predictors will be group (treatment arm), time (categorical), and their interaction. The model will be adjusted for baseline FIQR score. A random intercept will be used to adjust for the patient effect and to accommodate the correlation among the repeated measurements from the same patients. Another random intercept will be used to adjust for the potential clustering effect for patients in a specific yoga or exercise group. The primary analysis will evaluate the difference in FIQR score between the two treatment arms at 3-months (the primary end point) using appropriate contrast in this model. The sustained effect of intervention will be evaluated using appropriate contrast for the difference in FIQR change from 3-month to 6-month in this model.

D9d. Secondary analysis of primary outcome

For the FIQR total score, we will also define the patients with more than 30% reduction as “responders.” We will then compare the probability of responders between treatment arms using a generalized linear mixed model with a logit link. The responding status of each patient at **1, 3, 6, and 9 months** will be used as the outcome variables. Main predictors are group (treatment arm), time (1, 3, 6, and 9 months), and their interaction. A significant coefficient of group indicates a significant odds ratio of being a responder between the two arms at each time point. Each of the three domains of the FIQR score will be analyzed in the similar way to the total score.

D9e. Analysis of secondary outcomes

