Since POYSE is not specifically powered for the secondary outcome, these results should be interpreted cautiously unless they are highly significant ($p < .001$). Pain severity as assessed by the Brief Pain Inventory will be analyzed using a repeated measurement ANCOVA model in the same way as the FIQR total score. BPI measurement at 1, 3, 6, and 9 months will be used as the response variable. Main predictors will be intervention group, time (categorical), and their interaction adjusted for the baseline BPI score. A random intercept of subject effect will be used to accommodate correlation within subject. Another random intercept of either a specific yoga or exercise group will be used to accommodate correlation within group (clustering effect for group delivered intervention).

Psychological symptoms: PHQ-9 score, GAD-7 will be analyzed using a repeated measurement ANCOVA model in the same way as the FIQR total score with repeated outcomes at 1, 3, 6, and 9 months as the response variables, the same set of main predictors and adjusted for baseline outcome measurement. The PTSD screening status will be analyzed using a generalized linear mixed model with a logit link. The main predictors will be intervention group, time (categorical) and their interaction adjusted for baseline PTSD screening status. PTSD severity from PTSD checklist for military will be analyzed similarly.

Other secondary outcome measures: The analytical strategy for other outcomes will be similar to the FIQR total score. These outcomes include SF-36, MFI, MOS Sleep Scale, Pain Catastrophizing Scale, Arthritis Self-Efficacy Scale, and PGIC.

We will employ several secondary analyses to assess the effectiveness of the treatment arms compared to each other in improving:

- Individual fibromyalgia symptoms (pain, fatigue, sleep quality, function)
- Health-related quality of life
- Patient global impression of change
- Pain beliefs and self-efficacy

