To estimate cost effectiveness, the dependent variable will consist of primary cost outcomes calculated from the VA health care system perspective. Having obtained the relevant VA healthcare utilization events, the healthcare event requires valuation, which is the task of assigning a reasonable market-level dollar for the expense amount. For each patient, outpatient events (visits, procedures, labs, medications, etc.) and inpatient DRGs and medical events (procedures, labs, medications, etc.) will be captured from these patient-specific administrative datasets. VHA databases provide sufficient outpatient and inpatient procedure and associated treatment classifications (by CPT-4, DRG and ICD-9 codes) to allow valuation. [name] has created similar datasets in other VA funded studies and publications. For health care utilization and the associated costs, we will compare inpatient days, outpatient visits, telephone care, number of prescriptions and radiographic tests. However, we may not be able to include inpatient costs because hospitalization may occur rarely during the 9 months of the trial and make estimates of between-group differences imprecise.

We will compare the two treatment arms with respect to total health care costs. Univariate, bivariate and regression techniques for repeated measures will be used to estimate the healthcare events and expenditure amounts. If cost data are skewed, log transformations will be performed prior to performing regression. An ANCOVA model will be used and contain treatment group (independent variable) and adjusted for comorbidities, age, and previous health care cost data collected at baseline as a covariate.

Costs will be reported in current year's dollars. Sensitivity analyses will be used to account for assumptions, including changes in intervention costs and changes in costs related to inpatient or outpatient services. If the interventions are found to be differentially more effective and costly, we will perform a cost-outcome analysis (i.e., incremental cost-effectiveness). We will estimate the effect of the interventions on the primary outcome (FIQR total score). The incremental cost to achieve a clinically meaningful decrease in FIQR total scores due to the interventions, i.e., the cost-effectiveness ratio, is calculated as the difference in intervention costs between the two treatment arms, divided by the difference in effectiveness between groups.

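### The cost, responder and PTSD-status models name no class effect, and the responder model lists no baseline FIQR; the plan should write both in

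*Combined protocol and SAP*

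**What the plan says.** D9a treats correlation among patients taught in the same class as possible, says there are no preliminary data on it, assumes an ICC of 0.02 and inflates the sample by 14%.

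The primary model in D9c adjusts for baseline FIQR and has a patient random intercept. On class it says: "Another random intercept will be used to adjust for the potential clustering effect for patients in a specific yoga or exercise group". The BPI model in D9e repeats the baseline score and both intercepts, and PHQ-9 and GAD-7 are to be handled in the same way as FIQR.

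Three models are described differently:

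- **Responder status (D9d).** A generalized linear mixed model with a logit link: "Main predictors are group (treatment arm), time (1, 3, 6, and 9 months), and their interaction". No random effect is named and baseline FIQR is not listed.
- **PTSD screening status (D9e).** Also a logit mixed model: "The main predictors will be intervention group, time (categorical) and their interaction adjusted for baseline PTSD screening status". Baseline status is in, but no random effect is named.
- **Health care cost (D9i).** "An ANCOVA model will be used and contain treatment group (independent variable) and adjusted for comorbidities, age, and previous health care cost data". No random effect of any kind is named.

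D9e ends by saying that the remaining secondary analyses will use techniques similar to those already described.

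**The concern.** All three outcomes come from patients taught in the same yoga or exercise classes. Class is nested in arm, so any between-class variance goes straight into the variance of the arm comparison. A patient random intercept handles repeated visits by one person but still treats classmates as independent. If the listed terms are what is fitted, the plan protects FIQR and BPI against clustering and leaves these three comparisons unprotected.

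Small p-values matter here, because D9e asks for caution with secondary outcomes unless they reach p < .001 and then adds a Bonferroni or FDR step.

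The baseline gap is a separate matter of efficiency. D9c justifies its ANCOVA by the power gained when baseline and follow-up are positively correlated, yet D9d does not use the same covariate, which is already collected.

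**Working it through.** **1. The plan's own figures.** Inputs from D9a: "The absolute score difference at 3 months is estimated to be approximately 7 points (6.79, 14% of 48.3"), and "Assuming a common standard deviation of 17.6 and using a two-sample t-test". Sidedness is not stated; I take 5% two-sided.

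- Normal approximation: n = 2(1.960 + 0.842)² × 17.6² / 6.79² = 105.5, so 106 per arm.
- Exact noncentral t: 106 per arm gives 79.8% power and 107 gives 80.2%. This reproduces the plan's 107.
- Design effect: 1 + (8 − 1) × 0.02 = 1.14, and 107 × 1.14 = 121.98, so 122 per arm.
- Attrition: 122 / 0.80 = 152.5, so 153 per arm and 306 in total.

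The sample size stands, and nothing below changes it.

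**2. If class is left out.** With m patients per class and intra-class correlation ρ:

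- DE = 1 + (m − 1)ρ
- shortfall in the reported standard error = 1 − 1/√DE
- true size of a nominal 5% test = 2[1 − Φ(1.96/√DE)]

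D7b gives 8 to 12 per yoga class, and D9a expects similar sizes in both arms. The row m = 6.4 is a class of 8 less 20% attrition. Only ρ = 0.02 comes from the plan, where it was assumed for sizing on FIQR. The other values are my assumed range.

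| ρ | m | DE | SE too small by | True size of 5% test |
|---|---|---|---|---|
| 0.005 | 6.4 | 1.027 | 1.3% | 5.3% |
| 0.02 | 6.4 | 1.108 | 5.0% | 6.3% |
| 0.02 | 8 | 1.14 | 6.3% | 6.6% |
| 0.02 | 12 | 1.22 | 9.5% | 7.6% |
| 0.05 | 8 | 1.35 | 13.9% | 9.2% |
| 0.05 | 12 | 1.55 | 19.7% | 11.5% |

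A beta-binomial simulation with no true effect, an assumed 30% response and ρ = 0.02 on the binary outcome gave 6.5% (15 classes of 8 per arm) and 7.6% (10 classes of 12). At ρ = 0.02, a nominal 0.001 test would run at about 0.0021 (m = 8) to 0.0029 (m = 12).

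**3. A smaller ICC on the binary scale.** Suppose 0.02 is the correlation of the underlying continuous score and 30% respond (assumed). The binary ICC is then about φ(z)²ρ / [p(1 − p)] = 0.348² × 0.02 / 0.21 = 0.0115. DE is 1.08 (m = 8) to 1.13 (m = 12), and the 5% test runs at 5.9% to 6.5%.

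**4. If baseline FIQR is left out of D9d.** I used a single-visit logistic simulation with 122 per arm, baseline mean 48.3, SD 17.6 and a 6.79-point arm difference. The assumed comparator mean is 41.7, about a 13.6% fall.

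| Assumed baseline to 3-month correlation | Power without baseline | Power with baseline | SE of log OR, without / with |
|---|---|---|---|
| 0.3 | 63% | 69% | 0.266 / 0.282 |
| 0.5 | 76% | 78% | 0.269 / 0.275 |
| 0.7 | 91% | 91% | 0.276 / 0.277 |

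The gain comes from a larger estimated log odds ratio (0.61 to 0.68 at correlation 0.3), not from a smaller standard error.

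**The case against.** The best defence is that these models are under-described and nothing has been removed from them. Both binary models are called mixed models, so some random effect is intended. In D9c, too, the sentence on main predictors lists only group, time and interaction, and the baseline term and both intercepts come in later sentences. The closing statement in D9e points back to earlier methods. So a reader might infer that the plan discards the class effect in D9d and D9e, but the text does not show that. What remains is that a patient intercept alone would satisfy the wording. The back-reference follows a list that does not name responder status or costs, and the cost ANCOVA sits outside it altogether.

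A reader might also infer that the plan asserts a class effect and that the intervals are therefore too narrow. The plan calls clustering only possible, and it gives no ICC for responder status, PTSD status or cost. The inflation is conditional, and step 3 shows it could be smaller for a binary outcome.

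A third tempting reading is that the responder effect is overstated because a logit mixed model gives a patient-conditional odds ratio. That is a different estimand, not a biased one, and D9d itself names an odds ratio as the quantity to be tested.

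Finally, baseline FIQR is not wholly unused, because it enters the responder definition through the percentage reduction. That is correct, and the gain from adding it is small.

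**Conclusion.** The point holds as a gap in specification with a modest, conditional consequence. It is clearest for the cost ANCOVA, which lists its terms and has no class effect. For the two binary models the random effects are unnamed, and a compliant analysis could ignore class.

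If class is ignored and an ICC of 0.02 carries over to these outcomes, nominal 5% tests run at about 6.6% to 7.6% for classes of 8 to 12. If the ICC is smaller, as it may be on the binary scale, the error is smaller. The 0.05 rows only illustrate sensitivity and have no source in the plan.

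Omitting baseline FIQR from the responder model loses about 0 to 5 points of power under the assumed correlations. It does not make intervals too narrow. Only secondary and economic analyses are affected, since the primary 3-month contrast already names baseline and both intercepts.

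**What to change.** - **D9d:** add baseline FIQR as a covariate, and name a patient and a class random intercept.
- **D9e, PTSD status:** name a patient and a class random intercept.
- **D9i:** add a class random intercept to the cost model, or obtain intervals by a bootstrap that resamples whole classes.

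The cost is a few sentences in the plan and a few lines of code. Class membership is already needed for the primary model and baseline FIQR is already collected. Intervals will be slightly wider where class is added, and the responder odds ratio becomes conditional on baseline FIQR. Showing response probabilities by arm beside the odds ratio would help readers, but that is an optional matter of presentation.

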Medications are often the first line of therapy for fibromyalgia, but are frequently associated with adverse effects and show modest treatment benefits in clinical trials and practice.⁷ Aerobic exercise programs have proven benefit, but adherence to exercise is difficult to maintain and can lead to exercise-induced pain and myalgias if performed incorrectly. While the literature supports psychological treatments such as cognitive behavioral therapy (CBT) for reducing the overall symptoms of fibromyalgia, access to therapists with fibromyalgia expertise is limited. For relief, patients often turn to complementary and alternative medicine when traditional treatments are not effective.⁸ Yoga has shown initial promise for relief of fibromyalgia symptoms; presumably because yoga combines the benefits of exercise with relaxation and mindfulness practices. However, few yoga studies in fibromyalgia exist and those conducted have involved small sample sizes and yoga has not been compared to other treatments. With these challenges and limitations in mind, research to develop and compare different treatments for fibromyalgia, especially in veterans, is urgently needed.

We believe other treatment options are needed when pharmacological management fails to relieve fibromyalgia symptoms for veterans. Our long-term research objective is to develop, test, and implement novel treatments that address barriers to effective fibromyalgia treatment and that can be practicably applied in VA care settings. The **Pain Outcomes comparing Yoga versus Structured Exercise (POYSE)** Trial is a 2-arm parallel group, randomized clinical trial. The POYSE trial will target **306 veterans** with fibromyalgia and will compare the effectiveness of a yoga-based intervention (YOGA) with that of a structured exercise program (SEP). The trial will last 9-months and participants will undergo comprehensive outcome assessments at baseline, **1, 3, 6, and 9 months**.

Study Aims:

- 1) **To compare the interventions' (YOGA vs. SEP) effects on overall fibromyalgia severity at 1 month (early response), 3 months (immediate post-intervention) and at 6 and 9 months (sustained effects)**
- 2) **To compare the interventions' effects on specific fibromyalgia symptoms (pain, sleep, fatigue), functional impairment, and related outcomes (quality of life, depression, anxiety)**
- 3) **To compare the cost-effectiveness of the interventions**

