recruitment site (VAMC vs. CBOC). Within strata, randomization with block sizes of 4 or 6 will be executed to ensure balance. Once an eligible participant has been screened, has signed informed consent, and has completed the baseline measures the research assistant ([name]) or project coordinator ([name]) will submit a request to randomize the eligible participant. The randomization program locates the first unassigned record in the randomization list and assigns the participant to the group designated in that record. The participant identifier and date are written to the record. To ensure allocation concealment, only [name] and [name] will have access to the randomization table, but will not conduct outcome assessments. [name] will remain blinded to group assignment. No one will be allowed access to the folder of the randomization assignment until all baseline measures have been completed.

D7. POYSE INTERVENTION DETAILS

The POYSE interventions will last 3 months. The length of follow-up and schedule of outcome assessments at **1, 3, 6, and 9 months** after the date of the first intervention session are to detect **three** types of treatment effects: 1) **“early response” (at 1 month)**; 2) immediate post-intervention benefits at 3 months; and 3) sustained benefits at 6 and 9 months post-randomization (3 and 6 months post-intervention).

D7a. Overview of Yoga-based intervention

The yoga intervention (**Appendix 1**) will consist of three treatment components: 1) in-person group yoga sessions taught by a yoga therapist; 2) a relaxation audio recording for home-use; and 3) a DVD recording to reinforce concepts taught during in-person yoga sessions. The yoga intervention will complement standard medical treatments for fibromyalgia. It will involve 12 weekly group sessions of 8-12 patients per group. Each yoga session will last approximately 90 minutes and will be led by [name], Yoga Therapist (YT), who has over 30 years of experience in teaching yoga and meditation techniques to the general public and medical patients, including veterans. [name] has trained in several schools of yoga, but draws most significantly from the *Sivananda* tradition. She has also received veteran-specific yoga training in a program called “Warriors at Ease.” [name] will be the lead yoga therapist, but will train and supervise other yoga therapists to enhance future implementation.

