Analytic techniques will be similar to those previously described. Since there will be a number of secondary outcomes, we will account for multiple-comparisons in analyses. We will use the Bonferroni approach to adjust for statistical significance threshold when the number of tests is less than 20. Otherwise, we will use the false discovery rate (FDR)¹²² to control the magnitude of false positives. We will also stratify our analysis based on a baseline depression status (PHQ-9). Our previous research indicated that 30% to 40% of patients will have clinically significant depression, which may adversely affect pain outcomes. Thus, depression is a potential moderator.

D9f. Missing data

Missing data are unavoidable in longitudinal studies. Based on our prior studies, we anticipate a possible dropout rate between 8% and 12%. However, we conservatively estimated a possible 20% drop out rate which is reflected in the sample size calculation. We will first run a logistic model with missing status as the response variable, intervention arm, patients’ demographic characteristics as covariates to check whether the missing status depends on the intervention group assignment and patient characteristics. Second, our linear mixed-effect model can accommodate missing-at-random (or

MAR which is assumed in many trials)¹²³ where no bias will be introduced by ignoring the missing-data mechanism. If drop-outs are Missing Not At Random (MNAR), meaning the likelihood of drop-out depends on an un-observed outcome, and the missing data mechanism is ignored, potential bias can be introduced. We will run sensitivity analyses using complete cases, last observation carried forward imputation, other multiple imputation methods including linear mixed-effect model, to compare results across these analyses to assess the robustness of the inference.

D9g. Economic evaluation

We will conduct cost effectiveness to determine if changes in health care utilization may offset the intervention costs between treatment arms. To conduct this analysis, we will use established methods¹²⁴ to estimate direct costs of the interventions and health care spending for study participants during the **9 month** trial period from the perspective of the VA.

D9h. Costing

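### D9d reads a single group coefficient as the responder odds ratio at every visit, although the model contains a group-by-time interaction

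*Combined protocol and SAP*

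**What the plan says.** D9d defines a responder as a patient whose FIQR total score falls by more than 30%. Responder status at 1, 3, 6 and 9 months is the outcome of a generalized linear mixed model with a logit link. The predictors are group, time and their interaction. The rule for reading the model is: "A significant coefficient of group indicates a significant odds ratio of being a responder between the two arms at each time point". D9d names no contrast, no reference visit and no coding, and does not say whether time is categorical.

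D9c uses the same three terms for the continuous FIQR score, with time categorical, but draws its inference from contrasts. One contrast gives the arm difference at 3 months. For the later effect: "The sustained effect of intervention will be evaluated using appropriate contrast for the difference in FIQR change from 3-month to 6-month in this model".

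Aim 1 separates the visits. It asks about "effects on overall fibromyalgia severity at 1 month (early response), 3 months (immediate post-intervention) and at 6 and 9 months (sustained effects"). D7 makes the same division into early, immediate and sustained effects.

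**The concern.** In a model with a group-by-time interaction, no single group coefficient describes the arm difference at every visit, unless all the interaction terms are zero. The D9d sentence would be right for a model without the interaction, but the interaction is included. It would also be right if it meant a separate group contrast at each visit, but it names one coefficient.

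The plan does not assume a constant arm difference. Its aims distinguish the visits, and D9c gives the change from 3 to 6 months its own contrast. The documents do not say in which direction the difference would move.

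Two errors are therefore possible. A sustained responder benefit at 6 or 9 months could be claimed from a coefficient that tests another visit. A real 3-month benefit could be missed because the coefficient tests month 1. Since the coding is not stated, software defaults could decide which visit is tested.

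**Working it through.** **1. What the coefficient estimates.** Code group 0/1 and write logit P = a + b·group + time_t + g_t·group. The log odds ratio at visit t is b + g_t.

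- Reference coding of time: b is the log odds ratio at the reference visit only.
- Sum-to-zero coding of time: b is the average log odds ratio over the four visits.
- Time entered as a number: b is the log odds ratio extrapolated to time zero.

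b equals the log odds ratio at every visit only if every g_t = 0.

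A small example with assumed rates: 25% responders on exercise at every visit, and 45% on yoga at month 1 but 25% afterwards. The true odds ratios at 1, 3, 6 and 9 months are 2.45, 1, 1 and 1. The group coefficient, as an odds ratio, is 2.45 with month 1 as reference, 1.00 with month 3 or 9 as reference, and 2.45^(1/4) = 1.25 with sum-to-zero coding. The same truth gives three different coefficients.

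**2. The plan's own design figures.** D9a uses a difference of 6.79, an SD of 17.6, 5% error (two-sided assumed) and more than 80% power. The normal formula gives 2 × (1.960 + 0.842)² × 17.6² / 6.79² = 105.5, so 106. The exact t-test gives 106.4, so 107, with 80.2% power. Then 107 × 1.14 = 121.98, so 122. Dividing by 0.80 gives 152.5, so 153 per arm and 306 in all. These figures reproduce. The plan gives no responder rates and no power for D9d, so the next step needs assumptions.

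**3. Illustrative responder rates.** Inputs from D9a: baseline mean 48.3 (SD 17.5), yoga afterwards 35.5, SD 17.6, exercise 35.5 + 6.79 = 42.29. Assumed: bivariate normal scores with pre-post correlation 0.5. A responder has post < 0.7 × pre.

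- SD of (post − 0.7 × pre) = √(17.6² + 0.49 × 17.5² − 1.4 × 0.5 × 17.5 × 17.6) = √244.2 = 15.63.
- 0.7 × 48.3 = 33.81.
- Yoga: Φ((33.81 − 35.5)/15.63) = 0.457.
- Exercise: Φ((33.81 − 42.29)/15.63) = 0.294.
- Odds ratio 2.02, log odds ratio 0.705.

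**4. How often the rule fires.** SE of the log odds ratio = √[1/(n·p₁q₁) + 1/(n·p₀q₀)]. I use n = 107 per arm (122/1.14, to allow for clustering) and n = 122. With n = 107 the SE is 0.288, and the two-sided rejection rate at 0.05 is Φ(0.705/0.288 − 1.96) = 0.688. With n = 122 it is 0.744.

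Pattern (a): month 3 is the reference visit and the effect has gone by month 9. Chance of declaring a 9-month difference:

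| Threshold | D9d rule, n = 107 to 122 | 9-month contrast |
|---|---|---|
| 0.05 | 69% to 74% | 5% |
| 0.05/4 | 48% to 55% | 1.25% |
| 0.05/19 | 29% to 35% | 0.26% |
| 0.001 | 20% to 25% | 0.1% |

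Pattern (b): month 1 is the reference visit, with half the effect at month 1 (odds ratio 1.43) and all of it from month 3. The rule is met in 23% to 26% of trials at 0.05 and in about 2% at 0.001. The 3-month contrast is significant in 69% to 74% and 20% to 25%.

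**5. Sensitivity.**

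- Correlation 0.3: odds ratio 1.83; pattern (a) 57% to 62% at 0.05, 12% to 15% at 0.001.
- Correlation 0.7: odds ratio 2.42; 85% to 89% and 38% to 46%.
- Average coding in pattern (a), with shares 1, 1, 0.5 and 0 of the 6.79 points at the four visits: 58% to 64% at 0.05, 13% to 17% at 0.001.

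**6. Check in the mixed model itself.** Simulation of a random-intercept logit model, 1000 trials per setting, correlation 0.6 between post-baseline scores, no class effect, n = 107 and 122. Pattern (a): month 3 significant in 71.5% and 76.0%, month 9 in 3.8% and 4.7%. Pattern (b): month 1 in 22.1% and 23.1%, month 3 in 67.9% and 74.4%. This agrees with step 4.

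**The case against.** The intended analysis can be guessed. The sentence speaks of a comparison between arms at each time point. D9c handles the same terms with contrasts, and the logit model for PTSD status in D9e carries no such reading rule. A careful statistician would probably compute visit-specific odds ratios anyway. That is fair, but it is an inference: D9d states a different rule, and D9c's contrasts are specified for the linear FIQR model.

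Aim 1 is answered mainly by the continuous score, which D9c summarizes by arm at each time point. A false 9-month responder claim would sit beside those summaries. This limits the harm but does not correct the rule.

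The multiplicity language may temper claims. D9e says: "Since POYSE is not specifically powered for the secondary outcome, these results should be interpreted cautiously unless they are highly significant", with p < .001 as the mark. It adds: "We will use the Bonferroni approach to adjust for statistical significance threshold when the number of tests is less than 20", with a false discovery rate otherwise. The plan does not say whether either covers D9d. A stricter threshold lowers the error rates, but it does not change what the coefficient estimates.

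The size depends on choices the plan does not make. With month 9 as the reference, the false 9-month claim in pattern (a) falls to the nominal rate, and the error becomes a missed 3-month effect. The correlation is assumed, so the range in step 5 belongs with the result. D9a also calls the fall from 48.3 to 35.5 a 31% reduction, whereas (48.3 − 35.5)/48.3 = 26.5%. A true 31% fall would give 51% against 34% responders and an odds ratio of 2.01, so the illustration barely moves. These points stand as limits on the size. They do not touch the algebra.

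**Conclusion.** The sentence is wrong as written, and no other section repairs it. This follows from the model's terms and needs no assumed figure.

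The size is illustrative. Depending on the unstated coding, the rule can declare an absent 9-month difference in well over half of trials at 0.05, and in 12% to 46% at p < .001 with month 3 as reference and correlations from 0.3 to 0.7. It can also miss a 3-month difference in about three quarters of trials, where the correct contrast would miss it in about 26% to 31%. Both results rest on the assumed visit patterns and on bivariate normal scores. With a constant odds ratio the rule does no harm.

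The point should be fixed, but it is confined to a secondary analysis.

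**What to change.** Delete the sentence in D9d. Replace it with text to this effect:

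> Time will be categorical, as in D9c and D9e. The odds ratio between arms at 1, 3, 6 and 9 months, with its confidence interval, will be estimated from the contrast group plus group-by-visit.

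Two optional additions: name 3 months as the main responder comparison, in line with the primary endpoint, and state which of the thresholds in D9e applies to D9d.

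The cost is two sentences. No new data are needed, and the primary analysis and the sample size of 306 do not change.
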